MDA at Week 16 is the 5th endpoint in the sequential testing hierarchy (Table 7-4).

8.2.1.5 ACR20 and ACR70 response at Week 16

The ACR20 and ACR70 responses are defined based on respectively 20% and 70% or greater improvement from Baseline in the same measures than the primary endpoint. See Section 8.1.1 for details.

8.2.1.6 Proportion of subjects with an Investigator’s Global Assessment (IGA) score of 0 (clear) or 1 (almost clear) AND at least a 2-grade reduction from Baseline at Week 4 and Week 16 in the subset of subjects with psoriatic skin lesions at Baseline

A static IGA for psoriasis will be used to assess disease severity in all subjects during the study. Investigator will assess the overall severity of PSO using the following 5-point scale specified in Table 8-3 .

Table 8-3: Five-point IGA

Score	Short description	Definition
0	Clear	No signs of PSO; post-inflammatory hyperpigmentation may be present
1	Almost clear	No thickening; normal to pink coloration; no to minimal focal scaling
2	Mild	Just detectable to mild thickening; pink to light red coloration; predominately fine scaling
3	Moderate	Clearly distinguishable to moderate thickening; dull to bright red, moderate scaling
4	Severe	Severe thickening with hard edges; bright to deep dark red coloration; severe/coarse scaling covering almost all or all lesions

IGA=Investigator’s Global Assessment; PSO=psoriasis

The IGA response is defined as clear [0] or almost clear [1] assessment with at least a two-grade category improvement from Baseline, meaning that this parameter will be only evaluable for subjects with psoriatic skin lesions (IGA score ≥ 2) at Baseline.

Note that per protocol and device setting, only subjects with BSA $\geq 3\%$ at Baseline will have IGA assessed at post-Baseline visits.

For some subjects with BSA $\geq 3\%$ at Baseline, IGA data have not been captured at Week 4 and Week 16 visits when BSA $< 3\%$ at those visits. To address that, additional supportive analyses will be performed in which these subjects will be considered as IGA responders at the respective visit.

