8.3.1.8 Very Low Disease Activity (VLDA) response

Like MDA, VLDA is a state of disease activity deemed a useful target of treatment by both the subject and physician, given current treatment possibilities and limitations.

A subject is considered as having VLDA if all 7 of the criteria used for MDA and listed in [Section 8.2.1.4](#) are fulfilled. If any of the 7 criteria is not met, then the subject is considered as non-responder.

VLDA response will be analyzed at Week 4, 8, 12 and 16.

8.3.1.9 Proportion of subjects with an IGA score of 0 (clear) or 1 (almost clear) AND at least a 2-grade reduction from Baseline in the subset of subjects with psoriatic skin lesions at Baseline

Method for derivation of this variable can be found in [Section 8.2.1.6](#).

The proportion of subjects with an IGA score of 0 (clear) or 1 (almost clear) AND at least a 2-grade reduction from Baseline in the subset of subjects with psoriatic skin lesions at Baseline will be analyzed at Week 4, 8, 12 and 16.

For some subjects with BSA $\geq 3\%$ at Baseline, IGA data have not been captured at some post-Baseline visits when BSA $< 3\%$ at those visits. To address that, an additional supportive analysis will be performed in which these subjects will be considered as IGA responders at the respective visit.

In this context of this analysis, observed data for % of BSA affected by PSO will also be analyzed by visit using descriptive statistics.

8.3.1.10 Disease Activity Index for Psoriatic Arthritis (DAPSA) score categories, state and change from Baseline in DAPSA score

Disease Activity Index for Psoriatic Arthritis is a composite score of patient global and pain VAS, TJC, SJC and hs-CRP that incorporates a pattern of peripheral arthritis that often is encountered in PsA. DAPSA score will be calculated as follows:

$$DAPSA = SJC + TJC + PGA - Arthritis (VAS) + PtAAP (VAS) + hs - CRP$$

where:

- SJC ranges from 0 to 66
- TJC ranges from 0 to 68
- PGA-Arthritis represents the patient's global assessment of arthritis ranging from 0 to 10; 0=best, 10=worst (using the unrounded VAS that ranges from 0 to 100 mm and dividing this value by 10) (Refer to [Section 8.3.1.24](#)).
- PtAAP VAS ranges from 0 to 10 0=best, 10=worst (unrounded, by dividing the original value by 10)
- hs-CRP in mg/L (no upper limit applied).

DAPSA values will be categorized in the following disease activity states:

- Remission (REM) (DAPSA ≤ 4),
- Low Disease Activity (LDA) (DAPSA from >4 to ≤ 14),

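### The supportive IGA rule counts every visit with uncaptured IGA and BSA below 3% as a response, including cases the SAP's own IGA scale rules out, and is not labelled as an upper bound

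*SAP*

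**What the plan says.** Section 8.2.1.6 defines IGA response as "clear [0] or almost clear [1] assessment with at least a two-grade category improvement from Baseline" and adds that "this parameter will be only evaluable for subjects with psoriatic skin lesions", which it specifies as a Baseline IGA of 2 or more. Only subjects with Baseline BSA of at least 3% "will have IGA assessed at post-Baseline visits".

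The section then reports a gap within that group: for some subjects "IGA data have not been captured at Week 4 and Week 16 visits when" BSA was below 3% at those visits. The remedy is that "additional supportive analyses will be performed in which these subjects will be considered as IGA responders at the respective visit". Section 8.3.1.9 repeats it for the by-visit endpoint at Weeks 4, 8, 12 and 16: "an additional supportive analysis will be performed in which these subjects will be considered as IGA responders at the respective visit".

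Neither section makes the assignment depend on Baseline IGA, on whether BSA is 0 or merely below 3%, or on PASI. Neither says how the result should be read next to the NRI analysis.

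**The concern.** BSA and IGA measure different things. BSA is the extent of skin affected. The grades in Table 8-3 describe thickness, colour and scaling. A rule that turns low extent into IGA 0/1 with a two-grade drop needs support from the IGA definitions, and for one group of subjects those definitions contradict it.

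At stake is the reading of a named secondary variable (IGA response at Weeks 4 and 16) and its by-visit counterpart. The SAP presents the rule as the answer to the capture gap, so a reader of the study report could take its response rates as the corrected estimate. They are the most favourable assignment possible, and they include some assignments that are not possible.

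**Working it through.** No figure for IGA appears in the SAP, so the check is a logical one.

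**Inputs.** Response requires a post-Baseline score of at most 1 and a drop of at least 2 (8.2.1.6). Baseline IGA must be 2, 3 or 4 (8.2.1.6 with the five-point scale of Table 8-3). Score 0 means "No signs of PSO; post-inflammatory hyperpigmentation may be present" (Table 8-3). BSA is the percentage of body surface affected by psoriasis (8.3.1.9). The rule applies when IGA is uncaptured and BSA at that visit is below 3%.

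**Step 1: which post-Baseline scores qualify.** For Baseline score b and visit score x, response needs x ≤ 1 and b − x ≥ 2, that is x ≤ min(1, b − 2).

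- b = 2: x ≤ min(1, 0) = 0, so only 0 qualifies.
- b = 3: x ≤ min(1, 1) = 1, so 0 or 1 qualifies.
- b = 4: x ≤ min(1, 2) = 1, so 0 or 1 qualifies.

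**Step 2: what the visit BSA says about the score.** BSA of 0 means no affected skin, which corresponds to score 0. BSA above 0 means some psoriasis is present, which excludes score 0. It says nothing about thickness, colour or scaling, so it does not separate score 1 from 2, 3 or 4.

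**Step 3: compare with the rule.**

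| Baseline IGA | Visit BSA | What the definitions imply | Supportive rule |
|---|---|---|---|
| 2 | 0 | Responder | Responder |
| 2 | above 0, below 3% | Non-responder (needs 0, which is excluded) | Responder |
| 3 or 4 | 0 | Responder | Responder |
| 3 or 4 | above 0, below 3% | Undetermined (needs score 1) | Responder |

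The rule agrees with the definitions in two rows, contradicts them in one, and takes the most favourable value in one. Baseline IGA 0 or 1 is not a source of error, because the evaluable set excludes it.

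**Step 4: position relative to NRI.** Under 4.2.2.1 and 8.2.2, missing binary data count as non-response, so NRI scores all four rows as non-responders. For the visits in this gap, NRI is therefore the lower bound on each arm's response rate. The supportive rule lies at or above the upper bound: at it if there are no second-row visits, above it otherwise. These are bounds on the response rates, not on the treatment difference.

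**The case against.** The strongest reply concerns weight. IGA response is outside the testing hierarchy in section 4.5, its p-values are nominal under 8.2.2, and the analysis is additional and supportive. Sections 4.2.1.6 and 8.2.3 already plan NRI, a modified composite analysis with multiple imputation, and observed cases for such endpoints. IGA is listed among the variables to be imputed (4.2.1), so the all-responder version does not stand alone. Section 8.3.1.9 also summarises observed BSA by visit alongside it. And 3% is not an arbitrary level in this SAP: the MDA skin criterion in 8.2.1.4 accepts BSA up to 3%. All of this stands and limits the importance of the point. It does not remove the contradiction with Table 8-3, because low skin activity for MDA is not the same as IGA 0, and the SAP nowhere says the analysis is an upper bound.

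A reader might go further and infer that measurement noise around 3% creates a sizeable share of responders, since 3% is also the Baseline threshold for IGA assessment and a change from 3.0% to 2.9% would qualify. The documents do not support a size. With assumed lognormal BSA (median 3%, 5% or 8%, log-SD 1.0), assumed visit error (log-SD 0.1 to 0.4) and no true change, simulation puts 1.7% to 16.9% of subjects with Baseline BSA of at least 3% below 3% later. That tenfold spread comes entirely from the assumptions. The simulation also ignores the Baseline IGA requirement and treats IGA as uncaptured at every such visit, whereas the SAP says this happened for some subjects.

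A reader might also infer that the rule favours bimekizumab. The rule applies to both arms, and the direction of any effect on the comparison cannot be determined from the SAP.

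**Conclusion.** The point holds as a defect of definition in a supportive analysis. By the SAP's own scale, a subject with Baseline IGA 2 and BSA above 0 but below 3% cannot be an IGA responder, yet the rule in 8.2.1.6 and 8.3.1.9 counts one. For Baseline IGA 3 or 4 with BSA in the same range, response is possible but not shown, so the result is an upper bound.

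The conclusion rests only on the response definition, Table 8-3 and BSA being the area affected by psoriasis. It needs no assumption about the BSA distribution. The number of affected visits, their split by Baseline IGA, and BSA measurement error are not in the SAP, so no size of effect can be given. Type I error control, the primary endpoint, the hierarchy and the NRI analysis of IGA are untouched.

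**What to change.** In both 8.2.1.6 and 8.3.1.9, for visits with uncaptured IGA and BSA below 3%:

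1. BSA = 0: score IGA 0, responder.
2. BSA above 0 and Baseline IGA 2: non-responder.
3. BSA above 0 and Baseline IGA 3 or 4: keep the responder assumption.
4. State that the resulting rates are an upper bound for this gap, and report them beside NRI as the lower bound.

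Adding concurrent BSA, and PASI where captured, to the already planned multiple imputation of IGA is optional. As described in 4.2.2.2.1, that model contains only the strata and the variable's own visit values. The gap lies where BSA is below 3%, so the model may extrapolate, and the SAP does not say whether PASI was recorded at those visits.

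The cost is a wording change in two sections and a small programming change, using Baseline IGA and visit BSA that the SAP already uses. The downside is slightly lower supportive IGA response rates.

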8.2.1.7 Change from Baseline in the Patient's Assessment of Arthritis Pain (PtAAP)

The change from Baseline at Week 16 in PtAAP will be analyzed as described in [Section 8.1.4.4](#).

8.2.1.8 Change from Baseline in PsAID-12 total score at Week 16

The PsAID questionnaires measure the impact of disease on the subject. The impact of PsA is measured by weighting 12 different domains of health to derive a weighted summary score. The domains are pain, fatigue, skin problems, work and/or leisure activities, functional capacity, discomfort, sleep disturbance, coping, anxiety/fear/uncertainty, embarrassment and/or shame, social participation, and depression. The PsAID score is based on the relative importance of each of the domains. Each domain is answered based on a Numeric Rating Scales (NRS) scale ranging from 0 to 10.

The equation for the PsAID-12 scores is as follows:

$$PsAID - 12 = \frac{1}{20} (3 \times Pain + 2 \times Fatigue + 2 \times Skin + 2 \times Work/Leisure + 2 \times Functionnal + 2 \times Discomfort + 2 \times Sleep + Coping + Anxiety + Embarrassment + Social + Depression)$$

The total score ranges from 0 to 10 with higher scores indicating a worse impact of the disease. A score below 4 out of 10 is considered a subject-acceptable status. A change of 3 or more points is considered relevant absolute change.

If one value (from the 12 domains) is missing, the missing value will be imputed in taking the mean value of the remaining (non-missing) domains, and the imputed value will be used to calculate the PsAID with the formula above. If two or more of the domains are missing, the PsAID score will be set to missing.

8.2.1.9 Psoriasis Area Severity Index 90 (PASI90) at Week 4 (in subjects with PSO involving at least 3% of BSA at Baseline)

This variable will be derived as described in [Section 8.2.1.2](#).

8.2.2 Primary analysis of secondary efficacy variables

The secondary efficacy variables will be analyzed for all subjects in the RS.

As indicated in [Table 7-4](#), there are 4 secondary endpoints included in the testing hierarchy that will be tested in a chronological order until one is failed to be statistically significant.

For the other secondary endpoints (which are not part of the testing hierarchy), the p-values produced by the statistical models will be considered nominal since these endpoints are not controlled for multiplicity.

For the secondary composite and non-composite binary endpoints, the same estimand structure (composite estimand) as the one defined for the primary efficacy analysis of the primary efficacy endpoint ([Section 8.1.2](#)) will be used. The NRI approach for handling missing data and the same analysis model will be considered, and the analysis results will be presented similarly.

The statistical hypothesis for the binary variables at Week 16 is that the conditional odds ratio in the BKZ group compared with placebo treatment group is equal to 1. For the secondary continuous endpoints, the analysis will evaluate the hypothetical estimand as defined below:

- Population = Subjects enrolled according to the protocol-specified inclusion/exclusion criteria and randomized to IMP.
- Subject level outcome = variable as stated in [Section 2.2.2](#)
- Intercurrent event handling = An intercurrent event is defined as discontinuation of study treatment prior to Week 16. A hypothetical strategy for addressing intercurrent events will be implemented. This estimand targets the treatment difference in a scenario where withdrawal from study treatment does not occur, such that outcomes for subjects without an IE are as observed, and outcomes for subjects with an IE are treated as though they had completed treatment through Week 16 but on placebo. A MI strategy will be used to impute any missing data and observed data after IE which will be set to missing prior to running MI. Such data will be imputed using Reference-Based MI, in which the MI model is based on data from the placebo group.
- Population-level summary measure = the difference in the adjusted means between BKZ 160mg Q4W and placebo.

The same analysis model and imputation strategy for handling missing data as in [Section 8.1.4.4](#) will also be considered. The analysis results will be presented similarly as for this analysis on the individual ACR components.

In the case of MDA as the response is based on 7 different component scores, it is necessary to consider various data scenarios that could impact the calculation of response. The rules described here are applicable in the context of the calculation of MDA response and may differ from the rules applied for calculating and summarizing the components individually (some values may need to be imputed for component analysis but are not required here to evaluate MDA response).

The following rules will be applied to complete the derivation of MDA response based on the composite estimand definition:

- If a given visit has been preceded by an IE (treatment discontinuation):
 - The endpoint at all subsequent visits (whether the data were observed or not) will be set to “nonresponse” as the subject has not met the criteria for response.
- If a given visit has not been preceded by an intercurrent event:
 - If a subject satisfies at least 5 of the 7 MDA criteria, the subject is considered as MDA responder
 - If a subject does not satisfy at least 3 MDA criteria, the subject is considered as non-responder
 - In all other cases, the NRI approach will be applied.

An overview table will combine the results of the primary analysis for the primary and secondary efficacy endpoints included in the testing hierarchy.

For the country specific analyses performed on subjects randomized in Japan, the region factor will not be considered as a covariate for the modelling.

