2.4 Determination of sample size

Approximately 390 subjects will be randomly assigned in a 2:1 ratio to the following treatment groups: BKZ 160mg sc Q4W (260 subjects) and placebo (130 subjects).

The primary efficacy analysis is based on the primary comparison of BKZ versus placebo for ACR50 response at Week 16.

All sample size and power calculations were done at a significance level of 0.05.

All sample size and power calculations were performed using the software nQuery Advisor® 7.0.

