For MDA at Week 16, it is assumed that 5% of the placebo subjects achieve MDA at Week 16 (SPIRIT-P2 Week 12). Given the planned sample size and using a 2-sided 2-sample Chi-square test with continuity correction this study has 92% power to detect an absolute difference in MDA response at Week 16 of 12% (OR of 3.892) with a total sample size of 390 subjects.

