4 STATISTICAL/ANALYTICAL ISSUES

4.1 Adjustments for covariates

The primary efficacy analysis will investigate the treatment effect, adjusting on the 2 randomization stratification variables:

- Region
 - North America, Western Europe, Eastern Europe, Asiaor
 - North America, Eastern Europe, Western Europe + Asia if the percentage of randomized subjects is less than 10% in either of the Asia or Western Europe regions

- Prior TNF α inhibitor exposure (inadequate response to 1 prior TNF α inhibitor, inadequate response to 2 prior TNF α inhibitors, intolerance to TNF α inhibitors)

When adjusting on these 2 variables, a statistical model might not converge (ie, in case the likelihood maximization algorithm failed to converge). In that case, the statistical model will be run after dropping stratification variables in their order of appearance, successively region (one first and the other after) and prior TNF α inhibitor exposure.

In the event that a subject is stratified in the incorrect stratum (ie, the stratum recorded in the Interactive voice or web Response System (IXRS) differs from the actual stratum the subject belongs to), the actual stratum will be used for the analysis.

The secondary analyses will be adjusted on the same categorical factors as the primary analysis. For continuous variables, Baseline value (of the variable of interest) will also be included as covariate where appropriate.

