The norm-based T-scores for the 2 SF-36 component summary (PCS and MCS) and the 8 domains are standardized with a mean of 50 and a standard deviation (SD) of 10 in the general US population (Maruish, 2011). An individual respondent's score that falls outside the T-score range of 45 to 55 should be considered outside the average range for the US general population. When considering group-level data, a score below 47 should be considered indicative of impaired functioning within that health domain or dimension. Similar to individual respondent data, group mean scores of 47 or greater should be considered average or above average as compared to the general US population. Higher scores indicate a better health status.

For the calculation of the SF-36 norm-based T-scores for the 8 domains and the PCS and MCS, the scoring software Optum's PRO CoRE (version 1.4) will be used. The software uses updated 2009 U.S. population norms and applies a Full Missing Score Estimation method as follows:

- A health domain score (except the Physical Functioning domain) will be estimated provided that at least one non-missing response is available within that domain.
- For the Physical Functioning domain, item response theory will be used to develop a model for estimates of the missing score.
- Regression methods will then be applied to estimate the PCS and MCS on the basis of the available domains.

Change from Baseline at Week 16 in SF-36 PCS score is the 4th endpoint in the sequential testing hierarchy (Table 7-4).

8.2.1.4 MDA at Week 16

MDA is a state of disease activity deemed a useful target of treatment by both the subject and physician, given current treatment possibilities and limitations. The criteria that need to be met are based on key outcome measures in PsA and are shown below:

- Tender Joint Count ≤ 1
- Swollen Joint Count ≤ 1
- PASI ≤ 1 (for subjects with PSO involving at least 3% of BSA at Baseline) or BSA $\leq 3\%$
- PtAAP (VAS) ≤ 15 mm
- PGA-PsA (VAS) ≤ 20 mm
- HAQ-DI ≤ 0.5
- Tender enthesial points ≤ 1 (LEI ≤ 1)

A subject has achieved MDA if 5 or more of the 7 above criteria are fulfilled.

The enthesitis instrument of the study (ie., LEI) will be used to determine whether a subject has ≤ 1 tender enthesial point.

The following rule will be applied for subjects with BSA < 3 at Baseline: Subjects with BSA < 3 at Baseline will always meet the criteria PASI ≤ 1 or BSA ≤ 3 except in the cases where a post-Baseline BSA score > 3 is observed.

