8.3.1.12 Change from Baseline in all individual ACR core components

Individual ACR components (as listed in [Section 8.1.1](#)) are:

- SJC,
- TJC,
- HAQ-DI,
- PtAAP,
- PhGA-PsA,
- PGA-PsA,
- hs-CRP.

The change from Baseline (ratio from Baseline for hs-CRP) for each of the ACR components will be summarized at Week 4, 8, 12, and 16.

8.3.1.13 Enthesitis-free state based on the LEI and change in LEI from Baseline in the subgroup of subjects with enthesitis at Baseline

The Leeds Enthesitis Index (LEI) is an index composed of 6 items, 3 for the right part and 3 for the left part of the body that measures the severity of enthesitis. The body parts are lateral epicondyles of the humerus, medial femoral condyle, and Achilles tendons. Each item is scored for pain with either 1 (painful) or 0 (no pain). The total score ranges from 0 (no enthesitis) to 6 (severe enthesitis).

Note that LEI is collected for all subjects regardless of their Baseline score.

In case 4 items are missing, the LEI will be set to missing. If at least 3 items are available, the available items will be assessed and scored and then weighted by the number of the assessed items (AI) as shown in the formula below:

$$LEI = n \times \frac{\sum_{i=1}^n score}{\sum_{i=1}^n AI}$$

Note that n refers to the number of total items.

Enthesitis-free state is based on LEI of 0, for subjects with enthesitis at Baseline (LEI>0). Analyses on LEI will be restricted to the subset of subjects with enthesitis at Baseline (defined as LEI score>0).

The percentage of subjects with enthesitis free-state and the change from Baseline in LEI, in the subgroup of subjects with enthesitis at Baseline, will be analyzed at Week 4, 8, 12, and 16.

While not a secondary endpoint, to support the pooled endpoint in PA0010, enthesitis free-state at Week 16 will be analyzed using the same analysis method as the primary analysis.

8.3.1.14 Enthesitis-free state based on the SPARCC index and change in SPARCC index from Baseline in the subgroup of subjects with enthesitis at Baseline

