While not a secondary endpoint, to support the pooled endpoint in PA0010, dactylitis free-state at Week 16 will be analyzed using the same analysis method as the primary analysis.

8.3.1.16 Change from Baseline in the Bath Ankylosing Spondylitis Disease Activity Index (BASDAI) in the subgroup of subjects with axial involvement defined by a score of ≥ 4 at Baseline

The BASDAI measures the disease activity of ankylosing spondylitis. The BASDAI is a validated self-reported instrument which consists of 6 horizontal NRSs, each with 10 units to measure the severity of the following 5 major symptoms over the last week: fatigue, spinal pain, peripheral joint pain and swelling, enthesitis, and morning stiffness (both severity and duration) over the last week.

To give each symptom equal weighting, the average of the 2 scores relating to morning stiffness is taken. The resulting 0 to 50 sum score is divided by 5 to give a final BASDAI score between 0 and 10, with lower scores indicating lower disease activity.

The BASDAI is calculated as follows:

$$BASDAI = \frac{Q1 + Q2 + Q3 + Q4 + \left(\frac{Q5 + Q6}{2}\right)}{5}$$

where Q1 – Q6 are the six questions from the BASDAI questionnaire.

If 1 of the 2 morning stiffness measurements (ie, questions: “How would you describe the overall level of morning stiffness you have had from the time you wake up?” and “How long does your morning stiffness last from the time you wake up?”) is missing, the other one will be used for the morning stiffness calculation.

If one major symptom of the BASDAI is missing, the total score of the remaining symptoms will be divided by the number of symptoms assessed. If more than one major symptom is missing, the total BASDAI score will be set to missing.

Analyses will be restricted to the subset of subjects with axial involvement at Baseline (defined as BASDAI score of ≥ 4).

Change from Baseline in BASDAI will be analyzed for subjects with axial involvement at Baseline (BASDAI ≥ 4) at Week 4, 8, 12, and 16.

8.3.1.17 Change from Baseline in the modified Nail Psoriasis Severity Index (mNAPSI) score at Week 4, 8, 12 and 16 in the subgroup of subjects with psoriatic nail disease at Baseline

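### MDA (H5), the enthesitis- and dactylitis-free states and DAPSA low disease activity are absolute states analysed without a Baseline severity covariate: a modest, cheaply repaired loss of efficiency

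*SAP*

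**What the plan says.** SAP 8.1.2 defines the ACR50 model: logistic regression on treatment, prior TNFα inhibitor exposure and region. SAP 8.2.2 applies it to the secondary binary endpoints: "The NRI approach for handling missing data and the same analysis model will be considered". MDA at Week 16 is one of these and is H5 in the testing hierarchy (SAP 4.5).

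SAP 4.1 gives secondary analyses the same categorical factors as the primary and adds a Baseline term in one case only: "For continuous variables, Baseline value (of the variable of interest) will also be included as covariate where appropriate". H2 (HAQ-DI) and H4 (SF-36 PCS) are therefore Baseline-adjusted; H5 is not.

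The outcomes concerned are defined by where the subject ends up:

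- MDA (8.2.1.4): "A subject has achieved MDA if 5 or more of the 7 above criteria are fulfilled". All seven criteria are fixed thresholds. A subject with Baseline BSA below 3 is credited with the skin criterion unless a post-Baseline BSA above 3 is observed.
- Enthesitis-free (8.3.1.13) is LEI=0 among subjects with Baseline LEI above 0, and "enthesitis free-state at Week 16 will be analyzed using the same analysis method as the primary analysis".
- Dactylitis-free (8.3.1.15) is LDI=0 among subjects with Baseline LDI above 0, and "dactylitis free-state at Week 16 will be analyzed using the same analysis method as the primary analysis".
- DAPSA low disease activity or better is tested nominally with the same logistic model (8.3.2.3).

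**The concern.** ACR50 and PASI90 are percentage improvements, so Baseline is already part of the outcome and a model without a severity term is a natural choice. That reasoning does not carry over to an absolute state. A subject with LEI 1 has less far to go to reach 0 than one with LEI 6. A subject who already meets several MDA criteria needs fewer new ones.

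For MDA the dependence is partly written into the rule. SAP 2.4.2 assumes 50% of subjects have BSA of at least 3%, so about half start with one of the five required criteria credited by default. BSA is not a stratification factor (SAP 2.3.1), so its balance between arms is left to chance.

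Two things are at stake. One is some power, for a confirmatory hypothesis and for two states that support a pooled endpoint in PA0010. The other is a reported odds ratio that carries any chance imbalance in Baseline severity. Adjusting only after seeing such an imbalance would be post hoc.

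**Working it through.** **Inputs from the SAP (2.4, 2.4.2).** 260 BKZ and 130 placebo subjects. "All sample size and power calculations were done at a significance level of 0.05". For placebo, "it is assumed that 5% of the placebo subjects achieve MDA at Week 16". The MDA difference is 12 points, so 17% vs 5%. Stated odds ratio 3.892, stated power 92%, chi-square test with continuity correction.

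**Reproducing the stated power.** Take placebo p1 = 0.05, BKZ p2 = 0.17, allocation k = 2, d = 0.12, pooled p = (0.05 + 2×0.17)/3 = 0.13.

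- Odds ratio: (0.17/0.83)/(0.05/0.95) = 3.892.
- Null term: 1.96×√(0.13×0.87×1.5) = 0.807. Alternative term: √(0.05×0.95 + 0.17×0.83/2) = 0.344.
- Continuity correction: c = (k+1)/(k·d) = 12.5. Effective placebo n = (130 − 12.5/2)²/130 = 117.8.
- z = (0.12×√117.8 − 0.807)/0.344 = 1.44, so power is 92.5%. Without the correction (n = 130), z = 1.63 and power is 94.9%.

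The stated 92% is correct for the test named.

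**Effect of a Baseline covariate.** Model: logit P(response) = a(arm) + ln(OR_B)·x, with x standard normal and intercepts solved so that the marginal rates match the scenario. Two-sided Wald test at 0.05, 3000 simulated trials per row. OR_B, the 12% MDA rate, the subset sizes and the free-state rates are assumptions; the SAP gives none of them.

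| Scenario (BKZ vs placebo) | Subjects | OR_B per SD | Power without | Power with |
|---|---|---|---|---|
| MDA 17% vs 5% (planned) | 260/130 | 1.5 | 95.9% | 95.9% |
| | | 2 | 95.4% | 96.3% |
| | | 3 | 95.6% | 97.2% |
| | | 4 | 95.6% | 98.1% |
| MDA 12% vs 5% | 260/130 | 1.5 | 58.4% | 59.7% |
| | | 2 | 60.7% | 62.9% |
| | | 3 | 59.2% | 65.1% |
| LEI-free 55% vs 35% | 91/45 | 1.5 | 60.5% | 60.6% |
| | | 2 | 60.1% | 63.1% |
| | | 3 | 61.9% | 70.9% |
| LDI-free 75% vs 50% | 31/16 | 1.5 | 39.1% | 40.1% |
| | | 2 | 39.4% | 42.3% |
| | | 3 | 39.6% | 45.0% |

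The simulation standard error is about 0.4 points near 95% (√(0.95×0.05/3000)) and 0.9 points near 60%. With both MDA rates at 5%, the rejection rate was 3.0% to 4.3%, with or without the covariate.

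**The same check with the strata in the model.** I added three region and two prior-TNFα indicators (assumed shares 30/15/45/10% and 75/12/13%; 4000 trials per row). For OR_B of 1.5, 2 and 3:

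- MDA 17% vs 5%: 95.6% to 95.9%, 94.3% to 95.2%, 94.8% to 96.9%.
- MDA 12% vs 5%: 59.9% to 60.5%, 61.5% to 62.9%, 60.1% to 64.6%.
- Type I error stayed below 5%, and the number of fits that failed to settle was the same with and without the covariate.

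**Chance imbalance.** The SD of a standardised Baseline difference is √(1/130 + 1/260) = 0.107, so the 95% limit is 1.96×0.107 = 0.21 SD. An imbalance of that size shifts the unadjusted odds ratio by about exp(0.21×ln OR_B): 1.09, 1.16 or 1.26 for OR_B of 1.5, 2 or 3.

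**The case against.** The strongest defence is that nothing here is wrong. The SAP prespecifies adjustment for its two stratification factors and applies it consistently. Randomisation protects the test, and the confidence interval already allows for chance imbalance. At the planned MDA effect the gain is small, and at a Baseline odds ratio of 1.5 it is close to zero. No passage shows how prognostic Baseline severity is. All of that stands, and it limits the point to efficiency and precision.

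It can also be said that MDA is sparse. The planning rates imply 130×0.05 = 6.5 placebo and 260×0.17 = 44.2 BKZ responders, with up to five stratum parameters already in the model. The check with strata included showed no power loss and no extra non-convergence from one more term, so this does not carry the day. The simulated covariate is an idealised normal one. A real count of MDA criteria is a bounded integer, and because entry requires TJC and SJC of at least 3, two of the seven criteria will normally be unmet at Baseline.

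A reader might infer more than the document supports:

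- That H5 is underpowered or the 92% is wrong. It reproduces.
- That the unadjusted MDA test is invalid. Type I error is controlled either way.
- That the free states or DAPSA low disease activity are confirmatory. The free states are expressly not secondary endpoints, all three lie outside the hierarchy, and the DAPSA p-value is nominal.
- That VLDA needs the same change. It is only summarised as an unadjusted proportion, so there is no model to amend.

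**Conclusion.** The omission is real, and its consequence is a modest loss of efficiency and precision. For the one confirmatory endpoint affected, the gain from adjustment at the planned 17% vs 5% is about 0 to 2.5 points on a Wald power near 95%. At an assumed 12% vs 5% it was roughly 1 to 6 points in the runs shown, or about 0 to 7 allowing for simulation error. In the free-state subsets it ranged from nothing to about 9 points. Adjustment never lowered power materially.

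The upper ends need a strongly prognostic Baseline (odds ratio of about 3 or more per SD). Prognostic strength, subset sizes and free-state rates are all assumed. The benefit that does not depend on spare power is protection of the reported odds ratio against chance imbalance, worth a factor of about 1.09 to 1.26 at the 95% limit for MDA. Since the covariates are already collected and the term costs one degree of freedom, the change is worth making, but the analysis would be valid without it.

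**What to change.** Before unblinding, name one Baseline covariate per logistic model in SAP 4.1 and 8.2.2, with matching text in 8.3.1.13, 8.3.1.15 and 8.3.2.3:

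- MDA: number of the seven MDA criteria met at Baseline. Fix this one measure, with no alternative, because the test is confirmatory. DAPSA would be a poorer choice, as it contains no skin, HAQ-DI or enthesitis component.
- Enthesitis-free: Baseline LEI.
- Dactylitis-free: Baseline LDI.
- DAPSA low disease activity: Baseline DAPSA.

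Leave VLDA as it is.

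Two rules are needed with this. First, a missing Baseline covariate must not remove a randomised subject. After the Screening substitution in SAP 3.3, one simple rule is to count an unknown MDA criterion as not met and to give a missing Baseline DAPSA the median over both arms. The free-state subsets require a Baseline LEI or LDI above 0, so the question does not arise there. Second, place the covariate in the convergence drop order of SAP 4.1, for example last, after region and prior TNFα exposure.

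The cost is wording and one degree of freedom per model. The odds ratio becomes conditional on Baseline severity as well, so MDA would be conditioned on one more factor than ACR50 and PASI90 in the overview table, which a footnote can state. The free-state models should be kept aligned with the pooled PA0010 analysis, whose plan is not available here.
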